1. INTRODUCTION

The purpose of this reporting and analysis plan (RAP) is to update the list of displays to be included in the End of Study Clinical Study Report for Protocol:

Revision Chronology:		
2012N155299_00	2013-DEC-26	Original
2012N155299_01	2014-MAR-01	Amendment No. 1. Country specific Amendment for the United Kingdom to address required changes per MHRA. Updated Exclusion Criteria to exclude subjects with current corneal disease or history of corneal disease. Updated QTc withdrawal criterion to modify QTc withdrawal for QTc >500msec and to include > 60 msec increase from baseline. Updated Data Management Section 12 to include details on dissemination of data and communication plan.
2012N155299_02	2014-MAR-20	Amendment No. 2. Global Amendment to address required changes per the FDA. Updated Inclusion Criteria with minimum weight requirement. Updated Blood Volumes. Revised Time and Events Tables. Corrected typographical errors.
2012N155299_03	2014-MAY-05	Amendment No. 3. Country specific Amendment for Canada to address required changes per Health Canada. Updated preparation instructions of GSK2857916.
2012N155299_04	2016-MAY-05	Amendment No. 4. Global Amendment to include patient reported outcome instruments in the Part 2 multiple myeloma cohort and refine the lymphoma histologies eligible in Part 2 BCMA-expressing lymphoma cohort. Additionally, the requirement for 60% of tumor cells staining positive for BCMA expression was removed. The total number of subjects that may be enrolled is presented by a range of 80 to 95 to provide an updated estimate based on the number of subjects who enrolled at the time of the amendment. Additional modifications include: changing the time-point specific blood specimens are collected for baseline/pre-treatment immunogenicity and biomarker measurements, and the visit window for certain assessments.
2012N155299_05	2017-NOV-02	Global amendment to include additional follow up of multiple myeloma subjects for ocular exams (for those whose corneal signs or symptoms have not resolved), additional patient reported outcome instruments, addition of time-to-event endpoints as exploratory objectives. Subjects who have completed treatment or the 3 month follow up visit (end of study) prior to amendment 5 will be reconsented for further follow up and survival status. Other administrative changes are also included

1.1. RAP Amendments

Revision chronology: updated the list of displays (Appendix 12 of [RAP Amendment 1](#) for primary analysis) for multiple myeloma and lymphoma subjects to be included in the End of Study Clinical Study Report for Protocol. For multiple myeloma subjects, only displays with information that may significantly change after primary analysis are included. For lymphoma subjects, given the small number of subjects, the majority of the displays will be listings.

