2. SUMMARY OF KEY PROTOCOL INFORMATION

There are no changes to the planned analyses, analysis method and data handling convention as described in [RAP amendment 1](#). The only update is the list of displays for end of study analysis.

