30.0340	All Treated	SAFE_L2	Listing of Abnormal Slit Lamp Anterior Chamber and Slit Lamp Lens Exam Results (All Treated MM)	Report for sub-population: All Treated MM. Please include screening results and any post-baseline abnormal results for each patient. Include: Centre ID/ Subj., Age(y)/ Sex/ Race, Reported Corneal Events (Y/N), Cycle/Visit, Time Since 1st Dose/ Time Since last Dose, Eye, Exam Test, Result	EOS SAC
30.0341	All Treated	SAFE_L2	Listing of Abnormal Slit Lamp Anterior Chamber and Slit Lamp Lens Exam Results (Part 2 NHL)	Report for sub-population: Part 2 NHL. Please include screening results and any post-baseline abnormal results for each patient. Include: Centre ID/ Subj., Age(y)/ Sex/ Race, Reported Corneal Events (Y/N), Cycle/Visit, Time Since 1st Dose/ Time Since last Dose, Eye, Exam Test, Result	EOS SAC
30.0350	All Treated	SAFE_L2	Listing of Indirect Fundoscopic Exam and Intraocular Pressure Results (All Treated MM)	Report for sub-population: All Treated MM. Include: Centre ID/ Subj., Age(y)/ Sex/ Race,	EOS SAC

Non-ICH: Listings					
No.	Population	IDSL / Example Shell	Title	Programming Notes	Deliverable [Priority]
				Reported Corneal Events (Y/N), Cycle/Visit, Time Since 1st Dose/ Time Since last Dose, Eye, Exam Test, Result	
30.0351	All Treated	SAFE_L2	Listing of Indirect Fundoscopic Exam and Intraocular Pressure Results (Part 2 NHL)	Report for sub-population: Part 2 NHL. Include: Centre ID/ Subj., Age(y)/ Sex/ Race, Reported Corneal Events (Y/N), Cycle/Visit, Time Since 1st Dose/ Time Since last Dose, Eye, Exam Test, Result	EOS SAC
30.0810	All Treated	SAFE_L2	Listing of Visual Acuity and Abnormal Corneal Exam Results for Subjects with Ocular Exam Results in Follow-up (All Treated MM)		EOS SAC
30.0811	All Treated	SAFE_L2	Listing of Visual Acuity and Abnormal Corneal Exam Results for Subjects with Ocular Exam Results in Follow-up (Part 2 NHL)		EOS SAC
Health Outcomes					
30.0590	All Treated	VS4	Listing of Symptom Impact and HRQoL Item Scores (All Treated MM)	Report for sub-population: All Treated MM. Use the format of VS4, use collected visit dates. List scores for Bone Pain Worst, Bone Pain Average, Fatigue	EOS SAC
30.0591	All Treated	VS4	Listing of Symptom Impact and HRQoL Item Scores (Part 2 NHL)	Report for sub-population: Part 2 NHL. Use the format of VS4, use collected visit dates. List scores for Bone Pain Worst, Bone Pain	EOS SAC

Non-ICH: Listings					

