1.1. RAP Amendments

Revision chronology:

RAP Section	Amendment Details
Reporting and Analysis Plan_Study#_Final_V1 [26-JUN-2018]	
Reporting and Analysis Plan_Study#_Amendment_Final_V1 [Insert Date]	
Section 2.1 Changes to Protocol-Specified Analysis Plan	
 Clarified that EOI concentration is not Cmax for cys-mcMMAF Clarified definition of urine PK interval parameters Added analyte ratio determination and summaries
Section 5.2.2. Examination of Subgroups	
 Added a subgroup of "Penta-refractory", defined as refractory to: Bortezomib and Carfilzomib and Lenalidomide and Pomalidomide and Daratumumab. Accordingly, the existing forest plot described in Section 7.3.1.4 Subgroup Analysis of ORR (exploratory analysis) will also include this added subgroup.
Section 8.7. Other Safety Analyses (Ocular Exam)	
 Added summary of best corrected visual acuity (BCVA) at additional visits (i.e. the last follow-up exam) to existing displays. Added summary of subjects who experienced corneal clinical signs at additional visits (i.e. end of study treatment visit and last follow-up exam) to existing displays
Section 9.1.2.1. Noncompartmental Analysis	
 Clarified that EOI concentration is not Cmax for cys-mcMMAF Clarified definition of urine PK interval parameters
Section 9.3.1.1. Exploratory assessment of dose proportionality (PK analyses)	
 Clarified that dose proportionality assessment is based on Part 1 Cycle 1 data
Section 9.3.1.2. Assessment of Accumulation Ratio (PK analyses)	
 Clarified definition of accumulation ratio for consistency with study design Changed analyses from model approach to descriptive statistics
Section 9.3.1.3. Assessment of Analyte Ratios (PK analyses)	
 Clarified definition of analyte ratio for consistency with study design Changed analyses from model approach to descriptive statistics
Section 16.9.1. Population Pharmacokinetic (PopPK) Dataset Specification	
 Updated PopPK dataset specification
Section 16.10.1. Pharmacokinetic / Pharmacodynamic Dataset Specification	
 Updated PK/PD dataset specification

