Absolute change from baseline in LVEF will be summarized in the worst case post-baseline only. Only the post-baseline assessments that used the same method (ECHO or MUGA) as the baseline assessments will be used to derive the change from baseline. The change from baseline will be categorized as follows:

- No change or any increase
- Any decrease
- >0-<10 decrease
- 10-19 decrease
- \geq 20 decrease
- \geq 10 decrease and \geq LLN
- \geq 10 decrease and < LLN
- \geq 20 decrease and \geq LLN
- \geq 20 decrease and < LLN

LVEF results will also be listed with subject level details including absolute change from baseline.

Ocular Exams

For best corrected visual acuity (BCVA), if data is available, summary statistics for the logMAR score at baseline, end of study treatment and last follow-up exam will be displayed separately by eye using mean, median, standard deviation, minimum and maximum. Changes of logMAR score from baseline to end of treatment visit, last follow-up exam and maximum (worst) change from baseline will be summarized based on the following categories: no change/improved vision: a change from baseline <0.12 ; a possible worsened vision: a change from baseline ≥ 0.12 to <0.3 ; a definite worsened vision: a change from baseline ≥ 0.3 . Subjects with character values of visual acuity exam results will not be included in this summary.

Number and percentage of subjects who experienced corneal clinical signs will be summarized. Among subjects who experienced corneal clinical signs, number and percentage of subjects with/without reported corneal events will be provided. If data is available, the summary will also be provided at end of study treatment visit and last follow-up exam. Visual acuity/ abnormal corneal exam results (eye level) at each visit, and incidence of corneal clinical signs and reported corneal events (subject level) during the study will be listed. The findings considered 'corneal clinical signs' were identified from the pre-defined list of choices in the eCRF.

Listing of abnormal conjunctival exam results, listing of abnormal slit lamp Lens and slit lamp anterior chamber exam results and listing of indirect fundoscopic exam and intra-ocular pressure results will be provided separately.

Constitutional Symptoms (or B-Symptoms)

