13. HEALTH OUTCOMES ANALYSES

Symptom impact and HRQoL will be assessed using the e-Diary. The Pain (average and worst) and Fatigue (worst) items will be scored as individual items. Baseline will be calculated for each item as the mean of all of the assessments captured in the period prior to Cycle 1 Day 1 (treatment start date) (patients can only start the diary 2 to 4 days prior to Cycle 1 Day 1). There will be no minimum number of data points required to calculate a baseline, if only one day has been completed in this time period then this will be used as Baseline value.

Scores will be created for each pain (bone pain worst, bone pain average) and fatigue item (worst) during the treatment cycle. The mean for each item will be calculated from the available data for assessments on Day 1 through to Day 8 in each cycle (for a score to be calculated, at least 4 of the 8 days must be completed, otherwise data to be set to missing). For the assessment at Day 15 the stand-alone value will be the score for that item for that day. If not completed, then data for Day 15 is set to missing. Change from baseline for all pain and fatigue items will be assessed at each cycle. Change will be calculated for both time points (Day 1-Day 8 average and Day 15).

Visual Functioning Questionnaires (NEI VFQ-25 and OSDI): Data will be collected from end of treatment (EOT) visit as baseline. Additional data will be collected in follow-up visits on a monthly basis for subjects with ongoing corneal events or signs at EOT for 1 year or until resolution, whichever occurs first. These data will not be collected for subjects who already completed the treatment. Due to limited number of on-treatment subjects at the time of protocol amendment, only individual subject data will be listed. Data for both measures will be scored as outlined in the User Manuals.

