3.0653	All Treated	AE1	Summary of Adverse Events Leading to Dose Reductions, Interruptions or Delays, Permanent Discontinuation of Study Treatment by HLT (Part 2 NHL)	Report for: Part 2 NHL, (Summarize: only for 3.4 NHL)	SAC
3.0660	All Treated	AE3	Summary of Adverse Events Leading to Dose Reductions, Interruptions or Delays, Permanent Discontinuation of Study Treatment by Preferred Term (Part 1)	Report for: Part 1, (Summarize: by ascending dose level, Total).	SAC [A]
3.0661	All Treated	AE3	Summary of Adverse Events Leading to Dose Reductions, Interruptions or Delays, Permanent Discontinuation of Study Treatment by Preferred Term (Part 2 MM)	Report for: Part 2 MM, (Summarize: only for 3.4 MM)	SAC [A]
3.0662	All Treated	AE3	Summary of Adverse Events Leading to Dose Reductions, Interruptions or Delays, Permanent Discontinuation of Study Treatment by Preferred Term (All Treated MM)	Report for: All Treated MM, (Summarize: Total).	SAC [A]
3.0663	All Treated	AE3	Summary of Adverse Events Leading to Dose Reductions, Interruptions or Delays, Permanent Discontinuation of Study Treatment by Preferred Term (Part 2 NHL)	Report for: Part 2 NHL, (Summarize: only for 3.4 NHL)	SAC
Adverse Events of Interest					
3.0430	All Treated	OAE07	Summary of Corneal Events by Preferred Term and Maximum Grade (Part 1)	Report for: Part 1, (Summarize: by ascending dose level, Total).	SAC [A]
3.0431	All Treated	OAE07	Summary of Corneal Events by Preferred Term and Maximum Grade (Part 2 MM)	Report for: Part 2 MM, (Summarize: only for 3.4 MM)	SAC [A]
3.0432	All Treated	OAE07	Summary of Corneal Events by Preferred Term and Maximum Grade (All Treated MM)	Report for: All Treated MM, (Summarize: Total)	SAC [A]
3.0433	All Treated	OAE07	Summary of Corneal Events by Preferred Term and Maximum Grade (Part 2 NHL)	Report for: Part 2 NHL, (Summarize: only for 3.4 NHL)	SAC
3.0520	All Treated	ESI1	Summary of Characteristics of Corneal Events (Part 1)	Report for: Part 1, (Summarize: by	SAC [A]

CONFIDENTIAL

BMA117159

Safety: Tables					
No.	Population	IDSL / Example Shell	Title	Programming Notes	Deliverable [Priority]
				ascending dose level, Total). Summary based on both all subjects and subjects with events.	
3.0521	All Treated	ESI1	Summary of Characteristics of Corneal Events (Part 2 MM)	Report for: Part 2 MM, (Summarize: only for 3.4 MM). Summary based on both all subjects and subjects with events.	SAC [A]

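### The end-of-study display list re-runs the myeloma corneal and eye-exam listings but, without giving a reason, not the summary tables of the same data, including those planned for the last follow-up exam

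*SAP*

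**What the plan says.** The end-of-study RAP sets out its selection rule in section 1.1: "For multiple myeloma subjects, only displays with information that may significantly change after primary analysis are included". For lymphoma, the same section says that most displays will be listings because there are few subjects. No such reason is given for myeloma. Section 2 states that planned analyses, methods and data handling are as in RAP Amendment 1, and adds: "The only update is the list of displays for end of study analysis".

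RAP Amendment 1 plans the ocular summaries. Section 8.7 covers visual acuity (logMAR, by eye) at baseline, end of treatment and last follow-up exam, with change in categories that include a definite worsening of 0.3 or more. For corneal signs it says: "If data is available, the summary will also be provided at end of study treatment visit and last follow-up exam". The last-exam time point was added on purpose. The amendment log in section 1.1 of RAP Amendment 1 records: "Added summary of best corrected visual acuity (BCVA) at additional visits (i.e. the last follow-up exam) to existing displays". Section 8.2 plans onset and duration of the first corneal event, with duration grouped as 1-21, 22-42 and over 42 days.

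The exams that feed these tables are scheduled in section 16.2.3.1 (footnote 35). Part 2 myeloma subjects with corneal signs or symptoms at end of treatment are examined monthly for up to 12 months, or until the finding is stable or resolved.

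**The concern.** The rule and the list do not agree. If the follow-up eye listings are kept because their content may change materially, the summaries calculated from the same records can change too. The list keeps the first and omits the second. It also declares the analyses unchanged while giving the last-follow-up summaries of section 8.7 no end-of-study run.

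If eye follow-up continued after the primary cut, the only tabulated duration, persistence of signs and vision at last exam would be those from that cut. A corneal event still open then has no end date. Section 16.7.2.1 leaves a completely missing end date unimputed and the duration missing, so durations tabulated early would over-represent events that resolved quickly. A last exam at an early cut is likewise not the final one. The report would hold later recovery only as by-visit listings, for the first-named adverse event of interest in section 8.2, in a study whose primary objective is safety and tolerability.

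**Working it through.** No sample-size or error-rate figure is involved. The check compares table numbers and then dates.

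**Step 1: ocular summaries planned for myeloma.** RAP Amendment 1, section 16.12.8, has seven families, each for Part 1, Part 2 MM and All Treated MM:

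| Content | Tables |
|---|---|
| Corneal events by term and grade | 3.0430-3.0432 |
| Characteristics | 3.0520-3.0522 |
| Onset and duration | 3.0180-3.0182 |
| Leading to dose reduction | 3.0150-3.0152 |
| Leading to interruption or delay | 3.0160-3.0162 |
| Corneal clinical signs | 3.0490-3.0492 |
| Visual acuity (logMAR) | 3.0500-3.0502 |

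7 families x 3 = 21 tables.

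**Step 2: what the end-of-study list carries.** Section 4.1.4 has 31 safety tables, of which ten are titled for myeloma: 3.0030, 3.0031, 3.0060, 3.0061, 3.0700, 3.0701, 3.0131, 3.0141, 3.0570 and 3.0571. None is an ocular table, so 0 of 21 are carried forward.

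**Step 3: what is kept on the eye.** Sections 4.1.8 and 4.1.9 keep the myeloma listings of corneal events (1.0270), visual acuity and corneal exams (30.0260) and the same exams in follow-up (30.0810). They also keep the other eye-exam, eye-medication and questionnaire listings.

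**Step 4: what still refreshes in tables.** The general adverse event tables (3.0030, 3.0031, 3.0060, 3.0061) show every preferred term with maximum grade, so corneal terms are updated there without the grouping. For Part 2 MM, 3.0131 and 3.0141 likewise update corneal terms that led to dose reduction, interruption or delay.

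**Step 5: which omitted content depends on post-treatment exams.** Three items do so most: duration in 3.0181, signs at last follow-up in 3.0491, and acuity change at last follow-up in 3.0501. Baseline acuity is fixed, and time to onset is fixed for anyone who had already had a first event.

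**Step 6: was follow-up open at the primary cut?** No section says so. Two things point that way.

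- In section 4.1.3, treatment status for Part 2 MM (1.0021) is re-delivered unconditionally, while the Part 1 version (1.0020) is due only if its data change. Tables 3.0131 and 3.0141 are also refreshed for Part 2 MM. The list therefore expects Part 2 treatment data to move, and a subject still on treatment at the cut has not begun post-treatment eye follow-up.
- Protocol amendment 5, which added the extended eye follow-up, is dated 2 November 2017. Sections 16.9.1 and 16.10.1 mention a database cut in 4Q2018, assumed here to be the primary myeloma cut. For 365 days of follow-up to fit, the last dose had to fall by 1 October 2017 (cut on 1 October 2018) or 31 December 2017 (cut on 31 December 2018). A subject treated into 2018 could not have completed 12 months by then.

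**The case against.** The strongest reply is that the rule sets a threshold of significant change, which the sponsor is entitled to judge. If only a few subjects had follow-up exams, listing 30.0810 shows their recovery directly. Section 13 of RAP Amendment 1 describes the on-treatment group at the amendment as limited in number, and for that reason only lists the vision questionnaires. Section 3.3 places the final planned primary analyses after all participants have completed the study, while allowing a separate myeloma analysis before the lymphoma cohort completes. Footnote 35 lets exams stop early once an eye care professional finds the subject stable. The Part 1 schedule (section 16.2.2.1) has no monthly eye follow-up at all.

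Much of this stands. It means that neither the number affected nor a material change in the tables can be shown from the document. It does not explain why listings pass the threshold while summaries of the same records fail it, and the small-numbers reason is written for lymphoma only.

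A reader might infer that all ocular information is frozen at the primary cut. That goes too far: subject-level data are re-listed, and corneal terms and grades refresh in the general tables. A reader might also take the words "follow-up visits on a monthly basis for subjects with ongoing corneal events or signs at EOT for 1 year or until resolution" in section 13 as the exam schedule. They concern the questionnaires; the exam schedule is in section 16.2.3.1.

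**Conclusion.** The point holds as an inconsistency between the stated rule, the statement that analyses are unchanged, and the list. All 21 myeloma ocular summaries are absent, but the material part is three Part 2 MM tables: 3.0181 (duration), 3.0491 and 3.0501 (last follow-up exam). It would be wrong to treat all 21 as equally out of date.

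The practical effect rests on two assumptions: that eye follow-up was incomplete at the primary cut, and that this cut was the 4Q2018 one. The re-delivery of 1.0021, 3.0131 and 3.0141 supports the first, but a reader who takes it as established goes beyond the document. The number of subjects affected is not given. The cohort maximum of 40 (section 2.3) is a ceiling, not an estimate, and the true number may be small. This is a low-cost improvement to reporting, not a flaw that invalidates the safety analysis.

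**What to change.** Add 3.0181, 3.0491 and 3.0501 for Part 2 MM to section 4.1.4 of the end-of-study RAP with deliverable EOS SAC. Run them on the final database, and state in the report that they replace the primary-cut versions. List 3.0431, 3.0521 and the Part 1 and All Treated MM versions as due only if their data change after the primary analysis, the condition already attached to 1.0020. If the sponsor prefers not to add the three tables, section 1.1 should say why they cannot change significantly when the matching listings can.

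The cost is a few lines in the list and a re-run of shells that exist from RAP Amendment 1, with no new data. The downside is a little programming time and some tables that may barely differ from the first run.

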2. SUMMARY OF KEY PROTOCOL INFORMATION

There are no changes to the planned analyses, analysis method and data handling convention as described in [RAP amendment 1](#). The only update is the list of displays for end of study analysis.

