3.0323	All Treated	OLB9B	Summary of Hematology Grade Changes from Baseline Grade (Part 2 NHL)	Report for: Part 2 NHL, (Summarize: Total). Produce only for lab tests that are graded. For laboratory tests that are graded for both low and high values, summaries will be done separately and labeled by direction. Include only 'worst-case post-baseline'	EOS SAC
ECG					
3.0223	All Treated	VS1	Summary of Change from Baseline in Vital Signs (Part 2 NHL)	Report for: Part 2 NHL, (Summarize: only for 3.4 NHL) Add Cycle, Visit. Include baseline values.	EOS SAC
3.0373	All Treated	EG1	Summary of ECG Findings (Part 2 NHL)	Report for: All Treated MM, (Summarize for Total). Include baseline values.	EOS SAC
3.0393	All Treated	OECG1B	Summary of Worst-case Increases in Fridericia's QTc (Part 2	Report for: Part 2 NHL,	EOS SAC

CONFIDENTIAL

BMA117159

Safety: Tables					
No.	Population	IDSL / Example Shell	Title	Programming Notes	Deliverable [Priority]
			NHL)	(Summarize: Total). Include only 'worst-case post-baseline'	
3.0403	All Treated	OECG2B	Summary of Worst-case Amount of Increase from Baseline Value in Fridericia's QTc (Part 2 NHL)	Report for: Part 2 NHL, (Summarize: Total). Include only 'worst-case post-baseline'	EOS SAC
Death					
3.0570	All Treated	DTH1a	Summary of Deaths (Part 1)	Report for: Part 1, (Summarize: by ascending dose level, Total).	EOS SAC
3.0571	All Treated	DTH1a	Summary of Deaths (Part 2 MM)	Report for: Part 2 MM, (Summarize: only for 3.4 MM).	EOS SAC
3.0573	All Treated	DTH1a	Summary of Deaths (Part 2 NHL)	Report for: Part 2 NHL, (Summarize: only for 3.4 NHL)	EOS SAC
Anti-Drug Antibody					
3.0843	All Treated	SAFE_T 4	Summary of Human Anti-GSK2857916 Antibodies (ADA) Over Time (Part 2 NHL)	Report for: Part 2 NHL, (Summarize: only for 3.4 NHL)	EOS SAC
3.0853	All Treated	SAFE_T 5	Summary of Anti-GSK2857916 Antibodies (ADA) (Part 2 NHL)	Report for: Part 2 NHL, (Summarize: only for 3.4 NHL)	EOS SAC

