1.0140	All Treated	OAE04	Listing of All Adverse Events (All Treated MM)	Report for population subgroup: All Treated MM. Remove onset cycle and cycle day from all AE related listings.	EOS SAC
1.0141	All Treated	OAE04	Listing of All Adverse Events (Part 2 NHL)	Report for population subgroup: Part 2 NHL. Remove onset cycle and cycle day from all AE related listings.	EOS SAC
1.0150	All Treated	OAE03	Listing of Subject Numbers for Individual Adverse Events (All Treated MM)	Report for sub-population: All Treated MM.	EOS SAC
1.0151	All Treated	OAE03	Listing of Subject Numbers for Individual Adverse Events (Part 2 NHL)	Report for sub-population: Part 2 NHL.	EOS SAC
1.0160	All Treated	AE2	Listing of Relationship Between Adverse Event System Organ Classes, Preferred Terms, and Verbatim Text (All Treated MM)	Report for sub-population: All Treated MM.	EOS SAC
1.0161	All Treated	AE2	Listing of Relationship Between Adverse Event System Organ Classes, Preferred Terms, and Verbatim Text (Part 2 NHL)	Report for sub-population: Part 2 NHL.	EOS SAC

CONFIDENTIAL

BMA117159

ICH: Listings					
No.	Population	IDSL / Example Shell	Title	Programming Notes	Deliverable [Priority]
Serious and Other Significant Adverse Events					
1.0180	All Treated	OAE04	Listing of Fatal Serious Adverse Events (All Treated MM)	Report for sub-population: All Treated MM. Include column to indicate relationship to study treatment.	EOS SAC
1.0181	All Treated	OAE04	Listing of Fatal Serious Adverse Events (Part 2 NHL)	Report for sub-population: All Treated MM. Include column to indicate relationship to study treatment.	EOS SAC
1.0190	All Treated	OAE04	Listing of Non-Fatal Serious Adverse Events (All Treated MM)	Report for sub-population: All Treated MM. Include column to indicate relationship to study treatment.	EOS SAC
1.0191	All Treated	OAE04	Listing of Non-Fatal Serious Adverse Events (Part 2 NHL)	Report for sub-population: All Treated MM. Include column to indicate relationship to study treatment.	EOS SAC
1.0460	All Treated	AE14	Listing of Reasons for Considering as a Serious Adverse Event (All Treated MM)	Report for sub-population: All Treated MM.	EOS SAC
1.0461	All Treated	AE14	Listing of Reasons for Considering as a Serious Adverse Event (Part 2 NHL)	Report for sub-population: Part 2 NHL.	EOS SAC
1.0470	All Treated	OAE04	Listing of Adverse Events Leading to Withdrawal from Study / Permanent Discontinuation of Study Treatment (All Treated MM)	Report for sub-population: All Treated MM.	EOS SAC

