7.2.2.2. Summary Measure

Overall response rate and the associated 2-sided 95% exact confidence intervals will be provided. A list of investigator-assessed response at each visit will be listed.

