2.0342	All Treated	RE1a	Summary of Investigator-Assessed Best Response (With Confirmation) (RRMCL) (Part 2 NHL)	Report for population subgroup: Part 2 NHL. Summarize for 3.4 NHL. Best Response: Complete response (CR), Partial Response (PR), Minimal Response (MR), Stable Disease (SD), Progressive Disease (PD), Not Evaluable (NE). Overall Response Rate: (CR+PR).	SAC
Time-to Event Endpoint					
2.0081	All Treated	TTE1a	Summary of Duration of Response (Part 2 MM)	Report for population subgroup: Part 2 MM. Summarize: only for 3.4 MM. Do not include Hazard Ratio and Log-Rank P-Value. Only summarize for subjects with a confirmed PR or better.	SAC [A]
2.0201	All Treated	TTE1	Summary of Duration of Response for Subjects with Prior Daratumumab Treatment and Refractory to Both Immunomodulators and Proteasome Inhibitors (Part 2 MM)	Report for population subgroup: Part 2 MM. Summarize: only for 3.4 MM. Do not include Hazard Ratio and Log-Rank P-Value.	SAC [A]
2.0161	All Treated	TTE1	Summary of Duration of Response for Subjects without Prior Daratumumab Treatment (Part 2 MM)	Report for population subgroup: Part 2 MM. Summarize: only for 3.4	SAC [A]

CONFIDENTIAL

BMA117159

Efficacy: Tables					
No.	Populati on	IDSL / Example Shell	Title	Programming Notes	Deliverable [Priority]
				MM. Do not include Hazard Ratio and Log-Rank P-Value.	
2.0171	All Treated	TTE1	Summary of Duration of Response for Subjects Refractory to Both Immunomodulators and Proteasome Inhibitors (Part 2 MM)	Report for population subgroup: Part 2 MM. Summarize: only for 3.4 MM. Do not include Hazard Ratio and Log-Rank P-Value.	SAC [A]
2.0071	All Treated	TTE1	Summary of Progression-Free Survival (Part 2 MM)	Report for population subgroup: Part 2 MM. Summarize: only for 3.4 MM. Do not include Hazard Ratio and Log-Rank P-Value.	SAC [A]
2.0261	All Treated	TTE1	Summary of Progression-Free Survival for Subjects with Prior Daratumumab Treatment and Refractory to Both Immunomodulators and Proteasome Inhibitors (Part 2 MM)	Report for population subgroup: Part 2 MM. Summarize: only for 3.4 MM. Do not include Hazard Ratio and Log-Rank P-Value.	SAC [A]
2.0131	All Treated	TTE1	Summary of Progression-Free Survival for Subjects without Prior Daratumumab Treatment (Part 2 MM)	Report for population subgroup: Part 2 MM. Summarize: only for 3.4 MM. Do not include Hazard Ratio and Log-Rank P-Value.	SAC [A]

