2.0141	All Treated	TTE1	Summary of Progression-Free Survival for Subjects Refractory to Both Immunomodulators and Proteasome Inhibitors (Part 2 MM)	Summary of Progression-Free Survival for Subjects Refractory to Both Immunomodulators and Proteasome Inhibitors (Part 2 MM)	SAC [A]
2.0091	All Treated	TTE1a	Summary of Time to Response (Part 2 MM)	Report for population subgroup: Part 2 MM. Summarize: only for 3.4 MM. Do not include Hazard Ratio and Log-Rank P-Value.	SAC [A]

Efficacy: Tables					
No.	Population	IDSL / Example Shell	Title	Programming Notes	Deliverable [Priority]
2.0101	All Treated	TTE1a	Summary of Time to Progression (Part 2 MM)	Report for population subgroup: Part 2 MM. Summarize: only for 3.4 MM. Do not include Hazard Ratio and Log-Rank P-Value.	SAC [A]
2.0311	All Treated	TTE1a	Summary of Time to Best Response (Part 2 MM)	Report for population subgroup: Part 2 MM. Summarize: only for 3.4 MM. Do not include Hazard Ratio and Log-Rank P-Value.	SAC [A]
2.0321	All Treated	TTE6a	Summary of Kaplan-Meier Estimates of Overall Survival at 9 Months (Part 2 MM)	Report for population subgroup: Part 2 MM. Summarize: only for 3.4 MM. Produce if all the patients (who were alive at the time of study completion) can be re-consented.	SAC
2.0331	All Treated	TTE6a	Summary of Kaplan-Meier Estimates of Overall Survival at One Year (Part 2 MM)	Report for population subgroup: Part 2 MM. Summarize: only for 3.4 MM. Produced if all the patients (who were alive at the time of study completion) can be re-consented.	SAC

NOTES:

A. Indicates which displays will be generated for the reporting effort for multiple myeloma

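### The end-of-study display list has no table for the planned lymphoma response rate, and twelve lymphoma displays carry a programming note naming the myeloma population

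*SAP*

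**What the plan says.** The file holds two plans: the End of Study RAP and, behind it, RAP Amendment 1 (effective 06-NOV-2018), on which the first relies.

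- **End of Study RAP, section 2:** "There are no changes to the planned analyses, analysis method and data handling convention" from Amendment 1; only the list of displays is updated.
- **End of Study RAP, section 1.1:** two scoping rules. "For multiple myeloma subjects, only displays with information that may significantly change after primary analysis are included", and "For lymphoma subjects, given the small number of subjects, the majority of the displays will be listings".
- **Amendment 1, section 7.2.2.1.1:** the lymphoma response is a confirmed CR or PR. Confirmation comes from a repeat assessment at least four weeks later, and subjects who are not evaluable or have no response data count as non-responders. A summary of best response with confirmation is to be presented.
- **Amendment 1, section 7.2.2.2:** "Overall response rate and the associated 2-sided 95% exact confidence intervals will be provided".
- **Amendment 1, section 16.12.6:** table 2.0342 carries this analysis. Its deliverable code is SAC without the [A] that marks the myeloma reporting effort.
- **End of Study RAP, section 4.1.4, table 3.0373 (ECG findings, titled Part 2 NHL):** "Report for: All Treated MM, (Summarize for Total). Include baseline values".
- **End of Study RAP, section 4.1.8, listings 1.0181 and 1.0191 (fatal and non-fatal SAEs, titled Part 2 NHL):** "Report for sub-population: All Treated MM. Include column to indicate relationship to study treatment".

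**The concern.** A plan that says its analyses are unchanged should still contain a display for each of them. Lymphoma ORR is a secondary endpoint in Amendment 1, section 2.2. If the list is followed as written, the final report gives no confirmed rate and no interval for that cohort, while section 2 tells the reader that nothing was dropped.

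The programming notes are a second, separate matter. A programmer who follows the note rather than the title would place myeloma subjects under a lymphoma heading. The displays affected include the listings of fatal and non-fatal SAEs.

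**Working it through.** The plan states no figure to reproduce here. The check compares the two display lists and counts rows.

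**1. Is there any end-of-study display for lymphoma ORR?**

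- Sections 4.1.3 to 4.1.9 run without a gap: study population tables, safety tables, PK tables, PK figures, PK/PD figures, ICH listings, non-ICH listings. The number of efficacy tables or figures is 0, although section 4.1.1 still reserves the 2.xxxx and 12.xxxx ranges. The consecutive numbering argues against text lost in extraction.
- Table 2.0342 was outside the myeloma effort because it lacks [A]. Amendment 1, section 3.3, lets the myeloma analysis go ahead before the lymphoma cohort completes. Section 16.9.1 says the lymphoma data would not be fully cleaned at the 4Q2018 cut. End of study is therefore where 2.0342 falls due.
- What remains is listing 1.0561, investigator-assessed response by visit. It contains neither a derived confirmed best response, nor a rate on the full denominator, nor an interval.

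**2. How many displays have a population note that contradicts the title?**

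Titled Part 2 NHL, note All Treated MM:

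| Content | Displays | Count |
|---|---|---|
| ECG findings | table 3.0373 | 1 |
| Dose reductions, delays, escalations | 1.0101, 1.0111, 1.0121 | 3 |
| Fatal and non-fatal SAEs | 1.0181, 1.0191 | 2 |
| AEs leading to discontinuation, reduction, delay, incomplete or interrupted infusion | 1.0201, 1.0241, 1.0251, 1.0511, 1.0521 | 5 |
| ECOG status | 1.0431 | 1 |

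1 + 3 + 2 + 5 + 1 = 12. Listing 1.0430 (ECOG, All Treated MM) has the note Part 2 NHL, so 12 + 1 = 13 notes need correction. This is not a house convention: paired lymphoma listings such as 1.0141, 1.0491 and 1.0501 name Part 2 NHL correctly. All thirteen notes read the same way in Amendment 1.

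**3. What would the missing interval show?** (illustration only)

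The plan gives up to 10 lymphoma subjects and no assumed lymphoma ORR, so the response counts below are assumptions. For x responders out of n, the exact limits are the 0.025 quantile of Beta(x, n − x + 1) and the 0.975 quantile of Beta(x + 1, n − x). The lower limit is 0 when x = 0.

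| Assumed x/n | Exact 95% CI |
|---|---|
| 0/10 | 0% to 30.8% |
| 2/10 | 2.5% to 55.6% |
| 5/10 | 18.7% to 81.3% |

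**The case against.** **The ORR omission may be deliberate and matter little.** Section 1.1 announces mostly listings for a small cohort. Scans at cycles 4, 7, 10, 13 and 16 are 3 × 21 = 63 days apart, so a reader of listing 1.0561 could largely check the four-week confirmation by hand for at most 10 subjects. The interval would also be wide. This stands to the extent that the response data are not lost; a reader might infer that the endpoint disappears altogether, and it does not. It does not remove the contradiction. A majority of listings is not all listings, and the list keeps lymphoma summary tables for age ranges, race, past conditions, vital signs and anti-drug antibodies. Nothing in section 1.1 withdraws the ORR, and section 2 says no analysis changed.

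**The wrong notes do not show that section 2 is untrue.** A reader might take them as further undisclosed changes. They are inherited from Amendment 1, so they are specification errors left uncorrected.

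**Lymphoma safety is not left unanswered.** A reader might infer that it is. The same list has correctly specified lymphoma displays for all AEs (1.0141), SAEs (3.0703, 30.0541), deaths (1.0391), AEs leading to withdrawal or discontinuation (1.0471), AEs leading to reduction or delay (3.0133, 3.0143), overall dose modification (30.0131) and QTc (3.0393, 3.0403). The ECOG swap still yields both populations, under exchanged titles.

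**The missing OS displays are not a second lost analysis.** Tables 2.0321 and 2.0331 and listing 1.0580 are also absent, which makes that reading tempting. In Amendment 1 they depended on re-consent of all surviving patients. Section 7.3.1.2.6 provides a descriptive fallback, which the retained displays largely cover (3.0570, 3.0571, 1.0390, 1.0010, 1.0011). Leaving them out is consistent with an unchanged plan.

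**Conclusion.** The point holds in two parts of unequal weight.

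The main part is that one unconditional secondary analysis, the lymphoma confirmed best response and ORR with exact interval, has no display in the end-of-study list, while section 2 says planned analyses are unchanged. Both statements cannot be met. This assumes no separate lymphoma report was planned between the myeloma analysis and end of study; the documents mention none.

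The lesser part is thirteen inherited programming notes that contradict their titles, twelve on lymphoma displays and one on a myeloma listing. Read literally, they put the wrong patients under the title, but much of the content is correctly specified elsewhere in the list.

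The overall survival displays are not an error. The only gap there is that the End of Study RAP does not say whether the re-consent condition was met.

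**What to change.** 1. Add table 2.0342 to the end-of-study list. If the ORR summary is deliberately not tabulated, say so in section 2 with the reason.
2. Change the notes of 3.0373, 1.0101, 1.0111, 1.0121, 1.0181, 1.0191, 1.0201, 1.0241, 1.0251, 1.0431, 1.0511 and 1.0521 to Part 2 NHL, and the note of 1.0430 to All Treated MM.
3. Optionally, add one sentence on whether the re-consent condition for the OS displays was met.

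The cost is one table for at most 10 subjects and text edits to thirteen notes. No new data are needed.
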